Research procedures will be performed at Mount Sinai West Hospital and Mount Sinai Main Hospital. Screening evaluations will occur at FPA Urology practice locations and the Mount Sinai West Hospital Urology office.

[Type here]

Protocol Title:	A Phase I Single-Arm Open Label Dose-Escalation Study of CivaSheet with Radical Prostatectomy with or without Adjuvant External Beam Radiation Therapy in Patients with High Risk Prostate Cancer
Principal Investigator Name/Contact Info:	[name]/ [contact]/ [contact]
Primary Contact Name/Contact Info	[contact] [name]
Date Revised:	7/22/2022
Study Number:	GCO#1: 16-1314

2. Resources Available to Conduct the Human Research:

The operating surgeon's part of this study collectively perform 600 RP a year and expect to see 135 high-risk patients each year subject.

All personnel on the trial are adequately informed of the protocol and their role in all study related activities. All study personnel have completed CITI training requirements to conduct clinical research. Prior to active recruitment, the principal investigator will go through all aspects of the study with the study personnel. These aspects include the alternative standard therapy if the subjects were not part of this trial, the trial design, study rational, study related risks and benefits, the role of each personnel participating in the study, who to contact with any questions, and how to respond to situations or circumstances in which they are not accustomed to, or did not get briefed during the training session

3. Study Design:

A phase I single-arm open label dose-escalation study. This trial utilizes a 3+3 dose escalation design which will evaluate the MTD and, safety of CivaSheet® with a fixed dose of adjuvant EBRT (45 Gy) during RP in men with high risk PCa.

a) Recruitment Methods (see PPHS policy):

Source of potential subjects: Men with a diagnosis of NCCN high risk prostate cancer or NCCN intermediate-risk cancer with preoperative MRI evidence of extracapsular extension (ECE), seminal vesicle invasion (SVI) or N1 disease who are eligible to undergo RP with adjuvant EBRT as their definitive therapy.

Methods to identify potential subjects: All eligible subjects presenting to the PI or a Co-PI with a diagnosis of NCCN high-very high prostate cancer or NCCN intermediate high-risk cancer with preoperative MRI evidence of ECE, SVI or N1 disease are eligible to undergo RP with adjuvant EBRT as their definitive therapy who also meet inclusion will be consented by the PI or a Co-PI. If a potential subject then expresses interest in participating in the study, the physician/surgeon will present the potential subject with an informed consent form. All aspects of the trial will be discussed with interested subjects including the voluntary nature of their participation. Adequate time will be given to the subject to ask questions related to

[Type here]

Effective Date: 10/18/2022

End Date: 10/17/2023

Protocol Title:	A Phase I Single-Arm Open Label Dose-Escalation Study of CivaSheet with Radical Prostatectomy with or without Adjuvant External Beam Radiation Therapy in Patients with High Risk Prostate Cancer
Principal Investigator Name/Contact Info:	[name]/ [contact]/ [contact]
Primary Contact Name/Contact Info	[contact] [name]
Date Revised:	7/22/2022
Study Number:	GCO#1: 16-1314

the conduct of the trial. We will not advertise for this trial. Subjects will be recruited from the clinic.

b) Inclusion and Exclusion Criteria:

- Any subject with NCCN very high or high risk adenocarcinoma of the prostate defined as $\geq T3a$, Gleason score ≥ 8 , or PSA > 20 who is eligible for RP (open or robotic) with adjuvant EBRT as an initial treatment option.
- Any subject with NCCN Intermediate Risk adenocarcinoma of the prostate defined as T2b-T2c, Gleason score 7, or PSA 10-20 who is eligible for RP (open or robotic) with adjuvant EBRT as an initial treatment option and at least one of the following adverse features present in pre-operative imaging: SVI, ECE, N1 disease.
- Subject must have had a pre-operative MRI or must obtain a pre-operative MRI to be eligible for participation in this study.
- Ability to understand and the willingness to sign a written informed consent.

Exclusion Criteria

- Any subject who has undergone prior radiation to the pelvis.
- Subjects presenting with distant metastases.
- On any investigational drug(s), androgen deprivation therapy or therapeutic device(s) within 30 days preceding screening.
- Currently taking immunosuppressants, or with poorly controlled diabetes (HbA1c > 8).
- Subjects with prior treatment for PCa including BT, RT or hormone therapy.

c) Number of Subjects:

This is a 3+3 dose escalation design study to determine the MTD. This study will use 2 dose levels and 1-6 subjects at each dose level. The first subject enrolled at each dose level (60 and 75 Gy) will be monitored for the entire DLT window (3 months post EBRT completion) with subsequent subjects enrolled either at the same dose (if only 1 of the first 3 subsequent subjects at the given dose experiences DLT) or in the

[Type here]

Protocol Title:	A Phase I Single-Arm Open Label Dose-Escalation Study of CivaSheet with Radical Prostatectomy with or without Adjuvant External Beam Radiation Therapy in Patients with High Risk Prostate Cancer
Principal Investigator Name/Contact Info:	[name]/ [contact]/ [contact]
Primary Contact Name/Contact Info	[contact] [name]
Date Revised:	7/22/2022
Study Number:	GCO#1: 16-1314

next dose level if the preceding dose is deemed acceptable (i.e., < 33% DLT within 90 days post EBRT). If in the first subject, Grade 4-5 hematuria, fistula formation, proctitis or death occurs in the DLT window, the trial will be terminated. The total number of subjects for this single arm 3+3 trial design is therefore a minimum of 1 and a maximum of 12.

The dose escalation design utilized for the present study will proceed as follows: The first subject will be enrolled at 60 Gy. Once the entire DLT window (i.e., 90 days post EBRT) is complete for this first subject, the next 2 subjects will be enrolled at 60 Gy. If in the first subject, grade 4 or higher hematuria, proctitis, fistula formation or death occurs in the DLT window, the trial will be terminated. If 2 of the first 3 subjects experience DLT at 60 Gy, the trial will be terminated. If 0 or 1 of the first 3 subjects enrolled at 60 Gy experience a DLT after the third subject's entire DLT window is complete, an additional three subjects will be enrolled at 60 Gy. If $\geq 33\%$ of subjects experience DLT at 60 Gy, the trial will be terminated. If after the sixth subject's DLT window is complete and < 33% of subjects experience DLT at 60 Gy, the first subject at 75 Gy will be enrolled. Once the entire DLT window (i.e., 90 days post EBRT) is complete for this first subject at 75 Gy, the next two subjects will be enrolled at 75 Gy. If in the first subject at 75 Gy, grade 4 or higher hematuria, fistula formation, proctitis or death occurs in the DLT window, 60 Gy will be considered the MTD and no additional subjects will be enrolled at 75 Gy. If 2 of the first 3 subjects experience DLT at 75 Gy, 60 Gy will be considered the MTD and no additional subjects will be enrolled at 75 Gy. If 1 or 0 of the first 3 subjects enrolled at 75 Gy experience a DLT after the third subject's entire DLT window is complete, an additional 3 subjects will be enrolled at 75 Gy. If $\geq 33\%$ of subjects experience DLT at 75 Gy, no additional subjects will be enrolled at 75 Gy and 60 Gy will be considered the MTD. If after the sixth subject's DLT window is complete and < 33% of subjects experience DLT at 75 Gy, 75 Gy will be considered the MTD.

The true risk of toxicity is expected to be in the range of 10-50%. The following table shows the corresponding probabilities of dose escalation.

True Risk of Toxicity	0.1	0.2	0.3	0.4	0.5
Probability of Escalation	0.96	0.87	0.69	0.50	0.31

[Type here]

Protocol Title:	A Phase I Single-Arm Open Label Dose-Escalation Study of CivaSheet with Radical Prostatectomy with or without Adjuvant External Beam Radiation Therapy in Patients with High Risk Prostate Cancer
Principal Investigator Name/Contact Info:	[name]/ [contact]/ [contact]
Primary Contact Name/Contact Info	[contact] [name]
Date Revised:	7/22/2022
Study Number:	GCO#1: 16-1314

A minimum of 3 and a maximum of 6 subjects within a dose level must be observed for one cycle (90 day post EBRT completion) before accrual to the next higher dose level may begin.

Three patients within a dose level must be observed for one cycle (30 days post EBRT) before accrual to the next higher dose level may begin. The treatment for this study is RP + Civasheet implant + adjuvant EBRT for patients with high-risk or intermediate (non-clinically localized) prostate cancer with adverse pathologic features including seminal vesicle invasion, extra prostatic extension or a positive surgical margin. Since the clinical guidelines recommend adjuvant EBRT post RP only for patients with adverse pathologic features at RP, patients without these adverse pathologic features at RP will be replaced with additional patients at that dose level. Since however eligibility criteria is for high risk or non-clinically localized intermediate risk prostate cancer, the anticipated number of patients without these adverse pathologic features who will not receive adjuvant EBRT is 2 or less. While toxicities among these patients will be monitored according to the protocol, toxicities among these patients will not be used in determinations of the MTD. The MTD will only be determined for patients undergoing RP + Civasheet implant + adjuvant EBRT.

If a subject is withdrawn from the study prior to completing the entire cycle of therapy or prior to completing the entire DLT window without experiencing a DLT prior to withdrawal, an additional subject may be added to that dose level. Subjects missing doses due to a DLT will not be replaced since these subjects will be considered to have experienced a dose limiting toxicity.

d) Study Timelines:

The duration of an individual subject's participation in this study including follow-up is 5 years.

The expected duration for the investigators to complete this ranges between 1 month for a minimum of 1 subject and 44 months for a maximum of 12 subjects.

Table 1. Time and events table for those undergoing RP + Civasheet implant + adjuvant EBRT.

[Type here]

Effective Date: 10/18/2022

End Date: 10/17/2023

Protocol Title:	A Phase I Single-Arm Open Label Dose-Escalation Study of CivaSheet with Radical Prostatectomy with or without Adjuvant External Beam Radiation Therapy in Patients with High Risk Prostate Cancer									
Principal Investigator Name/Contact Info:	[name]/ [contact]/ [contact]									
Primary Contact Name/Contact Info	[contact] [name]									
Date Revised:	7/22/2022									
Study Number:	GCO#1: 16-1314									

	Pre-study	Day 1	Discharge (Typically Day 2)	1 Week	1 Month	6 Weeks	12 Weeks	23 Weeks	35 Weeks	Routinely for 4 years after Study completion
Assessment	X	X	X	X	X	X	X	X	X	X
Informed Consent, AE, Medical History/Medication s, Eligibility criteria, Pre-Surgical clearance (i.e., chest, EKG, etc.).	X									
Toxicity/ AE/ Complications (including DLT) Evaluations		X	X	X	X	X	X	X	X	X
X-Ray	X									
CBC	X	X	X							
Other required labs (PSA, testosterone, BMP)	X	X	X	X			X	X	X	
IIEF	X			X	X			X	X	X
MRI	X									
CT Scan			X		X		X		X	
Radical Prostatectomy + Civasheet Implant		X								
EBRT for 5 weeks						X				

Table 2. Time and events table for those undergoing RP + Civasheet implant without adjuvant EBRT.

	Pre-	Day	Discha	1	1	Routinel

[Type here]

Effective Date: 10/18/2022

End Date: 10/17/2023

Protocol Title:	A Phase I Single-Arm Open Label Dose-Escalation Study of CivaSheet with Radical Prostatectomy with or without Adjuvant External Beam Radiation Therapy in Patients with High Risk Prostate Cancer					
Principal Investigator Name/Contact Info:	[name]/ [contact]/ [contact]					
Primary Contact Name/Contact Info	[contact] [name]					
Date Revised:	7/22/2022					
Study Number:	GCO#1: 16-1314					

	study	1	age (Typically Day 2)	Week	Month	Year for 4 years after Study completion
Assessment	X	X	X	X	X	X
Informed Consent, AE, Medical History/Medication s, Eligibility criteria, Pre-Surgical clearance (i.e., chest, EKG, etc.).	X					
Toxicity/ AE/ Complications (including DLT) Evaluations		X	X	X	X	X
X-Ray	X					
CBC	X	X	X			
Other required labs (PSA, testosterone, BMP)	X	X	X	X		X
IIEF	X			X	X	X
MRI	X					
CT Scan			X		X	
Radical Prostatectomy + Civasheet Implant		X				

Assessments performed exclusively to determine eligibility for this study will be done only after obtaining informed consent. Assessments performed for clinical indications (not exclusively to determine study eligibility) may be used for baseline values even if the studies were done before informed consent was obtained.

All screening procedures must be performed within 30 days prior to registration unless otherwise stated. The screening procedures include informed consent, obtaining complete medical, surgical and infection history, demographic data, review of subject eligibility criteria, review of previous and concomitant medications, physical exam including height, weight and vital signs (temperature, pulse, respirations, blood pressure), baseline adverse event

Type here]

Protocol Title:	A Phase I Single-Arm Open Label Dose-Escalation Study of CivaSheet with Radical Prostatectomy with or without Adjuvant External Beam Radiation Therapy in Patients with High Risk Prostate Cancer
Principal Investigator Name/Contact Info:	[name]/ [contact]/ [contact]
Primary Contact Name/Contact Info	[contact] [name]
Date Revised:	7/22/2022
Study Number:	GCO#1: 16-1314

identification, complete blood count test, serum chemistries via a comprehensive metabolic pattern (including albumin, creatinine, etc.), an MRI prior to surgery if not already obtained prior to surgery and completion of the international index of erectile function questionnaire.

Procedures During Treatment

Prior to Treatment

- Physical exam, vital signs
- Hematology
- Serum chemistries

Day 1

- Radical Prostatectomy + Civasheet implant
- X-Ray for baseline assessment of Civasheet stability

1 week after RP + Civasheet Implant

- Physical exam, vital signs
- Hematology
- Serum chemistries
- Pathology Review
- JP Drain and Catheter removal

1 Months After RP + Civasheet Implant

- CT Scan for assessment of Civasheet stability, assessment of cancer recurrence and also for EBRT planning among those with adverse pathologic features who will undergo EBRT

3 and 6 Months After RP + Civasheet Implant

- CT Scan for assessment of Civasheet stability and assessment of cancer recurrence among those with adverse pathologic features who will undergo EBRT.

6 weeks after RP+ Civasheet Implant

- EBRT given at 45 Gy in 25 fractions for 5 weeks (Monday- Friday) among those with adverse pathologic features at EBRT.

[Type here]

Protocol Title:	A Phase I Single-Arm Open Label Dose-Escalation Study of CivaSheet with Radical Prostatectomy with or without Adjuvant External Beam Radiation Therapy in Patients with High Risk Prostate Cancer
Principal Investigator Name/Contact Info:	[name]/ [contact]/ [contact]
Primary Contact Name/Contact Info	[contact] [name]
Date Revised:	7/22/2022
Study Number:	GCO#1: 16-1314

90 Days after Completion of EBRT

- Assessment of cumulative DLT's to decide whether progression to next dose or termination of study is necessary.

Follow-Up:

- Subjects will be followed every 6 months after completion of study treatment for 4 years or if the subject withdraws consent from participation, the subject will not be followed-up. Subjects may be followed-up by telephone or contacted by phone to schedule Mount Sinai office visits to monitor for cancer recurrence and or cancer progression in addition to late toxicity.
- Subjects will be followed yearly after completion of study treatment for 4 years or if the subject withdraws consent from participation, the subject will not be followed-up. Subjects may be followed- up by telephone or contacted by phone to schedule Mount Sinai office visits to monitor for cancer recurrence and or cancer progression in addition to late toxicity.
- If patients are not scheduled for their follow-up visits with Mount Sinai Health System, the study team will call the patient to schedule a visit.
 - If the patient schedules a follow-up at Mount Sinai, appropriate measures will be assessed according to the protocol and data will be recorded.
- If the patient is seeing a physician outside of Mount Sinai Health System, we will request that their labs and physician notes are sent to us.
 - A research coordinator will review and record the outside labs and contact the patients to collect any missing information that can be obtained by phone (i.e. bleeding, incontinence, etc.)
 - A symptomology follow-up form, as well as an IIEF assessment form are attached.
 - If additional information is necessary to assess DLTs or AEs, a coordinator will call the patient and request they schedule a follow up visit at Mount Sinai. If the patient is unable to come in for a follow-up visit, they will be dropped the study.
 - If patients are not responsive after 2 attempts, they will be considered lost to follow up and replaced.

For those with adverse pathologic features: At 1 week post RP+ Civasheet

[Type here]

Protocol Title:	A Phase I Single-Arm Open Label Dose-Escalation Study of CivaSheet with Radical Prostatectomy with or without Adjuvant External Beam Radiation Therapy in Patients with High Risk Prostate Cancer
Principal Investigator Name/Contact Info:	[name]/ [contact]/ [contact]
Primary Contact Name/Contact Info	[contact] [name]
Date Revised:	7/22/2022
Study Number:	GCO#1: 16-1314

implant, 6 weeks after EBRT, 3 months after EBRT and 6 months after EBRT during the clinic visits, subjects will complete the IIEF to assess baseline erectile function following treatment. Subjects will undergo PSA testing for each follow-up visit. Those without adverse pathologic features not undergoing adjuvant EBRT will complete the IIEF to assess baseline erectile function following treatment and will also undergo PSA testing for each follow-up visit. Also at each follow-up visit or telephone follow up, subjects will be screened for toxicity and complications. The assessments may be done by phone when possible or lab results may be sent by the patient to our EMR if patient has followed up with an outside physician. For all patients, a CT-scan at day 0 (RP+Civasheet implant) will be done for a baseline stability assessment of the Civasheet. For all patients, a one month post-implant CT scan will be done of the pelvis for three purposes. The first purpose will be to perform a post-implant dosimetric analysis of the implanted Civasheet®. The bladder, rectum and any other identifiable structures (small bowel, large bowel or lymph nodes) will be outlined. The delivered dose will be calculated using a dose volume histogram and recorded. The second part of the CT will be to design the post-implant external beam radiation field among those who will undergo adjuvant EBRT. The third part will be to assess the stability of the Civasheet and any changes in position from initial implant. Among those who will undergo adjuvant EBRT, an additional post-implant CT scan at 90 days and 6 months will be done of the pelvis to prove stability of the device/implant method and to assess for cancer recurrence while those not undergoing adjuvant EBRT will not receive this imaging at 90 days and 6 months.

e) Specimen Banking for Future Uses Not Part of This Project:

NA

f) Data Storage, Transmission and Confidentiality:

To ensure data accuracy and completeness, random checks will be done by members of the research team listed in the protocol who are not directly responsible for data collection and entry. Data irregularities and errors will be collected and reported to the . Data collected and stored for current and future research use will include age, gender, [type here]

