hematuria, proctitis, or fistula are not observed. If 2 additional subjects are enrolled at 60 Gy, we will review for DLTs after completion of the 90 day DLT window and enroll 3 additional subjects at 60 Gy if DLT has been observed in 1 subject, or enroll 1 subject at 75 Gy if no DLT were observed or terminate the trial if $\geq 33\%$ DLT were observed in all subjects. For the next group of subjects at 60 Gy, we will review DLT/toxicity after all three subjects have completed the 90 days DLT window after EBRT. After the first subject's DLT window is complete (90 days post-EBRT) at 75 Gy, we will make a decision to enroll additional subjects at 75 Gy only if Grade 4-5 hematuria, proctitis, or fistula are not observed. If 2 additional subjects are enrolled at 75 Gy, we will review for DLTs after completion of the 90 day DLT window and enroll 3 additional subjects at 75 Gy if DLT has been observed in 1 subject, or terminate the trial if $\geq 33\%$ DLT were observed among the first three subjects at 75 Gy. For the next group of three subjects at 75 Gy, we will review DLT/toxicity after all three subjects have completed the 90 days DLT window. We will additionally describe rates of complications and toxicity (i.e., acute and late overall, GU and GI) by grade and by dose once the 6 month follow-up period is complete for all subjects. Toxicities among those not receiving EBRT will not affect the MTD determination or the decision to enroll additional patients at the same dose or at a higher dose. The DMC will review data at least once annually.

If the DMC recommends termination of the study we will terminate the study. If in the first subject at any dose Grade 4-5 hematuria, proctitis or fistula occur, we will terminate the study. If $\geq 33\%$ of subjects experience DLT (i.e., Grade 3 hematuria, proctitis, urinary retention) within the first 90 days post EBRT, the trial will be closed.

The Clavien-dindo classification of surgical complications will be used to assess complications and the NCI-CTCAE v4.0 in addition to the RTOG acute and late morbidity scoring criteria will be used to grade adverse events and toxicity.

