A Phase I Single-Arm Open Label Dose-Escalation Study of CivaSheet With Radical Prostatectomy With or Without Adjuvant External Beam Radiation Therapy in Patients With High Risk Prostate Cancer

[name]

NCT03657108

Document Date: 10-18-2022

**Primary Outcome:** We will determine the MTD for Civasheet when administered with RP and adjuvant EBRT. MTD is defined as the highest dose of the Civasheet® not yielding unacceptable toxicity. Specifically if > 33 % of subjects experience DLT at any dose level, the dose level below that level will be considered the MTD. Or if the highest level (75 Gy) has been reached and < 33% of subjects have experienced DLT, 75 Gy will be considered the MTD.. The present study defines dose limiting toxicity as the development of Grade 3 or higher (According to the NCI'S CTCAE v 4.0) urinary retention, hematuria or rectal bleeding/radiation proctitis within 90 days post EBRT which is given 6 weeks after RP + Civasheet implant for 5 weeks. Toxicities experienced among those not receiving adjuvant EBRT will not be used in the determination of the MTD. Binary or categorical outcomes will be described with proportion and 95% confidence intervals and continuous measures will be summarized with mean (SD) or median (IQR), as appropriate.

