While all genitourinary and gastrointestinal toxicities according to the NCI-CTCAE will be documented and evaluated every time a subject is seen Grade 3-5 hematuria, urinary retention and rectal bleeding/radiation proctitis are the specific toxicities used for dose escalation procedures. This study defines DLT as the development of NCI-CTCAE Grade >3 urinary retention, Grade 3 hematuria or Grade 3 rectal bleeding/radiation proctitis within 90 days post EBRT which is given 6 weeks after RP + Civasheet implant for 5 weeks. Grade 3 hematuria according to the NCI-CTCAE is defined as gross hematuria with indications including transfusion, IV medications, hospitalization, elective endoscopic, radiologic or operative intervention and limiting self-care activities for daily living. Grade 3 urinary retention is defined as an incomplete ability to empty the bladder with indications including elective operation or radiologic intervention, substantial loss of affected kidney function or development of mass. Grade 3 rectal bleeding/proctitis is defined as severe symptoms; fecal urgency or stool incontinence and limiting self-care activities for daily living. If > 33% of subjects experience these DLT at any dose, the dose level below that level will be considered the MTD. If  $\geq 33\%$  subjects experience a DLT at 60 Gy, the trial will be closed and no additional subjects will be enrolled. Also, if the first subject enrolled at 60 Gy experiences NCI-CTCAE Grade 4 or higher hematuria, fistula formation or proctitis, no additional subjects will be enrolled and the trial will be closed. If the first subject enrolled at 75 Gy experiences Grade 4 or higher hematuria, fistula formation or proctitis, no additional subjects will be enrolled at 75 Gy and 60 Gy will be considered the MTD. Grade 4 hematuria is defined as hematuria with life-threatening consequences and urgent radiologic or operative intervention indicated. Grade 4 or higher fistula (anal or urinary) formation is defined as a fistula with life-threatening consequences with urgent radiologic or operative intervention indicated. Grade 4 or higher proctitis is defined as proctitis with life-threatening consequences and urgent intervention indicated. The time frame for DLT evaluation is the first 90 days after EBRT. EBRT is given 6 weeks after RP+ Civasheet implant at 45 Gy in 25 fractions (Monday-Friday for 5 weeks). If > 33 % of subjects experience DLT at any dose level, the dose level below that level will be

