considered the MTD. Or if the highest level (75 Gy) has been reached and < 33% of subjects have experienced DLT, 75 Gy will be considered the MTD. If in the first subject treated at 75 Gy, NCI-CTCAE Grade 4 or higher hematuria, prostatitis or fistula formation occur, no additional subjects will be enrolled at 75 Gy and 60 Gy will be considered the MTD.

**Secondary:** We will describe the adverse events, toxicity and complication profile associated with Civasheet overall and at each dose when administered with RP and EBRT and also separately for those not receiving EBRT. Overall and for 60 and 75 Gy, the toxicity and complication profile associated with the Civasheet® will be assessed. Rates for surgical complications and adverse events, acute (< 90 days) and late (18 months days) GU and GI toxicity and adverse events using the NCI-CTCAE v4.0, RTOG Acute Toxicity Scale and Late Radiation Morbidity scales will be assessed. Erectile preservation and total urinary incontinence will be assessed overall and for each dose group once all subjects have completed the 6 month follow-up after EBRT. Peri- and post-operative complications associated with surgery will be assessed and graded using the Clavien-Dindo classification of surgical complications. Erectile preservation rates [IIEF score (erectile component) > 18] will be assessed, continence defined as the use of no pads will also be assessed. Binary or categorical outcomes will be described with proportion and 95% confidence intervals and continuous measures will be summarized with mean (SD) or median (IQR), as appropriate.

BCR defined as a post-prostatectomy serum PSA > 0.2 ng/ml will also be assessed for each subject. To evaluate cancer control, the Kaplan Meier-Method will be used to estimate BCR overall and for each dose group and separately for those receiving vs. not receiving EBRT once all subjects have completed the 6 months follow-up after EBRT or 6 months follow-up after Civasheet implant if no EBRT is given.

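### No prespecified rule uses toxicity after day 90 post EBRT in the count that opens 75 Gy or names the MTD, although some 60 Gy men will already have longer follow-up

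*Protocol*

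**What the plan says.** **Opening 75 Gy.** Protocol Section 3(c) allows the "next dose level if the preceding dose is deemed acceptable (i.e., < 33% DLT within 90 days post EBRT". The SAP's Primary Outcome sets the same limit: "The time frame for DLT evaluation is the first 90 days after EBRT".

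**Sequence at 60 Gy.** Section 3(c) treats 1, then 2, then 3 men. For the second step at this dose it says: "Once the entire DLT window (i.e., 90 days post EBRT) is complete for this first subject, the next 2 subjects will be enrolled at 60". The third step follows when 0 or 1 of the first three "experience a DLT after the third subject's entire DLT window is complete, an additional three subjects will be enrolled at 60 Gy". The last step is that "If after the sixth subject's DLT window is complete and < 33% of subjects experience DLT at 60 Gy, the first subject at 75 Gy" is to be enrolled. The safety-monitoring text that precedes the Adverse Events heading gives a different branch after three men: "or enroll 1 subject at 75 Gy if no DLT were observed".

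**MTD.** The SAP's Primary Outcome states: "MTD is defined as the highest dose of the Civasheet® not yielding unacceptable toxicity". The text that follows makes this specific as a percentage of men with DLT, and limits DLT to 90 days after EBRT.

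**Late toxicity.** The SAP's Secondary section plans rates for "late (18 months days) GU and GI toxicity and adverse events", with acute meaning under 90 days. The protocol follows men for 4 years. It plans to describe toxicity by grade and dose after every subject has finished the 6-month follow-up, which cannot be before 75 Gy opens if 75 Gy is used.

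**The concern.** Each group must finish its DLT window before the next is enrolled. The earliest 60 Gy men therefore accumulate follow-up beyond day 90 while the later ones are treated, and toxicity is recorded throughout. None of that information enters the numeric count that opens 75 Gy or names the MTD. A Grade 3 proctitis, hematuria or urinary retention first seen after day 90 leaves the count unchanged.

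Two things are at stake. The team may hold relevant safety data when 75 Gy opens without any stated requirement to set it out at that point. And an MTD quoted without its time limit would claim more than 90-day data can show.

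**Working it through.** **Inputs.** Implant to start of EBRT, 6 weeks = 42 days; EBRT, 5 weeks = 35 days (protocol, Procedures During Treatment; SAP, Primary Outcome). DLT window, 90 days (both documents). One month = 30.4375 days.

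- Implant to end of EBRT: 42 + 35 = 77 days.
- One group: 77 + 90 = 167 days = 5.49 months.

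**1. The plan's own duration.** Section 3(d) gives 44 months for 12 subjects. Six groups back to back take 6 × 167 = 1002 days = 32.9 months, so 44 is not reproduced. It would need 44/6 − 5.49 = 1.85 months of extra time per group, which the documents do not state. The no-gap times below are therefore minima.

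**2. Section 3(c) sequence.** 75 Gy opens on day 3 × 167 = 501. Time since EBRT = opening day − implant day − 77.

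| 60 Gy men | Implant day | Days since EBRT | Months |
|---|---|---|---|
| Subject 1 | 0 | 501 − 0 − 77 = 424 | 13.9 |
| Subjects 2-3 | 167 | 501 − 167 − 77 = 257 | 8.4 |
| Subjects 4-6 | 334 | 501 − 334 − 77 = 90 | 3.0 |

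Three of six men are past day 90. If the stated 44 months is spread evenly (44/6 = 7.33 months = 223.2 days per group), subjects 2-3 are at 90 + 223.2 = 313.2 days (10.3 months) and subject 1 at 90 + 446.4 = 536.4 days (17.6 months).

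**3. Safety-monitoring sequence, 0 of 3 with DLT.** 75 Gy opens on day 2 × 167 = 334. Subject 1 is at 334 − 77 = 257 days (8.4 months); subjects 2-3 are at 334 − 167 − 77 = 90 days. One of three men is past day 90.

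**4. When the MTD is named (Section 3(c), all 12 men, no gaps).** On day 1002 the 60 Gy men are at 1002 − 77 = 925, 1002 − 167 − 77 = 758 and 1002 − 334 − 77 = 591 days, that is 30.4, 24.9 and 19.4 months. All are beyond 18 months (548 days), if the SAP's garbled late time point is read as months. The 75 Gy men are at 424, 257 and 90 days.

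**5. What the count can miss.** On the Section 3(c) sequence, the three longer-followed men could each have a late Grade 3 event (3/6 = 50%) while the DLT count reads 0/6. This is a limit on what the rule can see, not a forecast.

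**6. Routes by which a late event could act.**

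| Route | Time limit | Reach |
|---|---|---|
| DLT count (Section 3(c), safety-monitoring text, Stopping Rules, SAP) | 90 days after EBRT | Men who receive EBRT |
| First-subject Grade 4-5 rule | DLT window in Section 3(c); none in the termination sentence of the safety-monitoring text, the Stopping Rules or the SAP | One man per dose |
| Monitoring committee (called DMC, DSMC and DSMB) | None | Discretionary; at least one review a year; none tied to opening 75 Gy |
| Adverse-event reporting | Attributed events more than 30 days after treatment are still reported | No stated link to the dose decision |

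The documents give no late Grade 3 or higher rate, so the calculation stops here.

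**The case against.** A reader might infer that late toxicity cannot affect the dose decision at all. The documents do not support that.

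- The committee can end the trial and its recommendations are binding. Unexpected events go to it, and notable safety findings at interim analysis interrupt the study. New or increased risks go to the IRB within 5 business days. None of this ends at day 90.
- Annual review is a minimum. Counting a year from the first implant with no gaps, a review on day 365 would see subject 1 at 365 − 77 = 288 days and subjects 2-3 at 365 − 167 − 77 = 121 days after EBRT. Late data would exist at a required review before day 501.
- The safety-monitoring text speaks of reviewing DLT and toxicity after the second group of three at 60 Gy, so the review may already look beyond DLT.
- The untimed versions of the first-subject rule would catch a late Grade 4-5 hematuria, proctitis or fistula in that man.

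These points stand, and they reduce the finding to the absence of a prespecified rule. They do not remove it. No committee review is tied to opening 75 Gy, the content of the toxicity review is undefined, and expected events are reported annually. Late Grade 3 events in any man, and late Grade 4 events in subjects 2-6, meet no stated rule.

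A reader might also infer that half the 60 Gy men will always have long follow-up. That holds only on the Section 3(c) sequence. It is also tempting to quote a chance that a late event has already occurred, but any such figure would rest on a rate the documents do not supply.

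Nor does the SAP hide the basis of the MTD: the sentences after its general definition tie it to 90-day DLT. Finally, a fixed window gives every man equal observation, which is a sound reason to leave the DLT definition alone.

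**Conclusion.** The point holds in limited form. The numeric rules for opening 75 Gy and naming the MTD use only events to day 90 after EBRT, and late toxicity is a descriptive secondary outcome. Later events can act only through committee discretion, general reporting, or a first-subject rule with inconsistent timing.

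The unused follow-up is at least 8.4 to 13.9 months in three of six men on the Section 3(c) sequence, or 8.4 months in one of three on the safety-monitoring sequence. Both assume the stated 6-week, 5-week and 90-day intervals and no recruitment gaps; the 30-day observation sentence in Section 3(c), if applied, would shorten them. No frequency of late toxicity is claimed. The 90-day window is not itself an error. This is a cheap improvement to the plan, not a flaw that invalidates the design.

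**What to change.** 1. **Review before 75 Gy (protocol Section 3(c) and the safety-monitoring text).** Add a cumulative table of the listed Grade 3 or higher toxicities, and Grade 4 or higher fistula, for every 60 Gy man from implant to the review date, with each man's length of follow-up. Give it to the monitoring committee. Leave the DLT definition, the window and the weight given to late events to the investigators and the committee.
2. **Statement of the result (SAP, Primary Outcome and Secondary).** Report the MTD as based on toxicity to 90 days after EBRT. Beside it, give cumulative Grade 3 or higher events by dose up to the date the MTD is named, with length of follow-up.
3. **Reconcile the text.** Three conflicts need settling: the time limit of the first-subject Grade 4-5 rule (Section 3(c) against the safety-monitoring text, Stopping Rules and SAP); when 75 Gy opens (after six men in the Section 3(c) sequence, or after three without DLT in the safety-monitoring text); and the 30-day and 90-day observation sentences in Section 3(c).

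The data are already collected. The cost is a small amount of extra reporting, a possible short wait while the committee sees the table, and a narrower headline claim.
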